### **Progression-free survival:**

- PFS
  - Time interval from the index date to the date of disease progression or death from any cause, whichever comes first
- PFS2
  - Time interval from the index date to the date of disease progression on second-line treatment or death from any cause, whichever comes first

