9.6 Date of last contact

The date of last contact will be derived for participants not known to have died at the analysis cut-off using the latest complete date prior to or at the data cut-off date among the following:

- All participant assessment dates (visit date, dates of assessment for vital signs, disease assessment as per imaging, NCCN-FACT FKSI-19)
- AE start and end dates
- Study drugs start and end dates
- Date of discontinuation on the Avelumab and/or Axitinib Termination or Study Termination eCRF pages (do not use if reason for discontinuation is lost to follow-up).

For PFS, PFS2 and DoR, a patient progressing after stopping current treatment and starting a new therapy will be censored at the latest tumor assessment showing no progression before changing therapy.

Only dates associated with actual examinations of the participant reported in the eCRF will be used in the derivation. Dates associated with a technical operation unrelated to participant status will not be used. Assessment dates after the cut-off date will not be applied to derive the last contact date.

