Table 4 Outcome and event dates for PFS

Scenario	Date of event/censoring	Outcome
PD or death before subsequent anti-cancer therapy	Date of PD or death	Event
PD or death after subsequent anti-cancer therapy	Date of last adequate tumor assessment ^a documenting no PD before subsequent anti-cancer therapy is given	Censored
No PD/Death	Date of last adequate tumor assessment ^a documenting no PD before subsequent anti-cancer therapy is given	Censored
Treatment discontinuation due to 'Disease progression' without documented progression	Not applicable	Information is ignored. Outcome is derived based on documented progression only.
Study end for consent withdrawn without PD or death	Date of last adequate tumor assessment ^a documenting no PD before subsequent anti-cancer therapy is given	Censored

	Study end for lost to follow-up without PD or death	Date of last adequate tumor assessment ^a documenting no PD before subsequent anti-cancer therapy is given	Censored
^a If there are no adequate post-baseline assessments prior to the PD or death, then the time without adequate assessment should be measured from the index date; if the criteria were met the censoring will be on the index date.			
PFS2	
PFS2 time is defined as the time from the index date to the date of disease progression on second-line treatment or death from any cause, whichever comes first. The tumor response will be determined according to RECIST v 1.1 and assessed by the investigator.
 
PFS2 time (in months) = (Date of PD or death after second-line treatment start – index date + 1) / 30.4375 (months).
 
PFS2 data will be censored on the date of the last adequate tumor assessment for participants who do not have an event (PD or death) or start a further subsequent anti-cancer therapy prior to an event. Participants who do not have any post-baseline tumor assessments will be censored on the start date.
 
The last adequate tumor assessment is defined as the last tumor assessment result that is not “NE” or “NA”.
 
The censoring and event date options to be considered for the PFS2 analysis are presented in below table.
 
PFS2 will be estimated by the KM method. The percentage of censored patients will also be reported. Median event time will be reported, along with 25th and 75th percentiles. Percentage of patients experiencing event or being event-free at applicable timepoints will also be reported along with the corresponding two-sided 95% CIs.
		

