
Table 5 Outcome and event dates for PFS2
			
Scenario	Date of event/censoring	Outcome	
PD or death after further subsequent anti-cancer therapy	Date of PD or death	Event	
PD before further subsequent anti-cancer therapy	Date of last adequate tumor assessment ^a documenting no PD after further subsequent anti-cancer therapy is given	Censored	

	No PD/Death	Date of last adequate tumor assessment ^a documenting no PD after further subsequent anti-cancer therapy is given	Censored		
	Treatment discontinuation due to 'Disease progression' without documented progression	Not applicable	Information is ignored. Outcome is derived based on documented progression only.		
	Study end for consent withdrawn without PD or death	Date of last adequate tumor assessment ^a documenting no PD after subsequent anti-cancer therapy is given	Censored		
	Study end for lost to follow-up without PD or death	Date of last adequate tumor assessment ^a documenting no PD after subsequent anti-cancer therapy is given	Censored		
^a If there are no adequate post-baseline assessments prior to the PD or death, then the time without adequate assessment should be measured from the index date; if the criteria were met the censoring will be on the index date.					
ORR	The ORR will be calculated along with the two-sided 95% CI using the Clopper-Pearson method. In addition, the frequency (number and percentage) of participants with BOR of CR, PR, SD, PD and NE will be tabulated. Investigator response will be used to determine the BOR up to 24 months derived as per documented BOR considering the order CR>PR>SD>PD. [REDACTED]				
DCR	DCR is defined as proportion of participants with BOR of CR, PR, SD and will be calculated along with the two-sided 95% CI using the Clopper-Pearson method. Investigator response will be used to determine the BOR up to 24 months derived as per documented BOR considering the order CR>PR>SD>PD. [REDACTED]				
DoR	DoR is defined, for participants with BOR CR or PR only, as the time interval from the first CR or PR criteria met, whichever was reported earlier, until the date of documented overall disease progression. BOR will be derived as documented BOR. [REDACTED] If a participant has not had the event, DoR is censored at the date of last adequate tumor assessment.				

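### The PFS2 event and censoring rules contradict the PFS2 definition and each other, and no single reading of the undefined therapy term reconciles them

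*SAP*

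**What the plan says.** The protocol (section 9.1.2.2) defines PFS2 as "Time interval from the index date to the date of disease progression on second-line treatment or death from any cause, whichever comes first", and SAP sections 5 and 14.2 repeat this. Death is not restricted to patients who have started second-line.

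Four further rules govern the derivation:

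- **Formula (SAP 14.2).** The end date is "Date of PD or death after second-line treatment start".
- **Prose (SAP 14.2).** Patients are censored at the last adequate tumor assessment if they have no event or "start a further subsequent anti-cancer therapy prior to an event".
- **Table 5 (SAP 14.2).** The only Event row is "PD or death after further subsequent anti-cancer therapy". The row "PD before further subsequent anti-cancer therapy" is Censored. For that row and for patients with neither PD nor death, the censoring date is the last adequate assessment "documenting no PD after further subsequent anti-cancer therapy is given". The withdrawal and lost-to-follow-up rows drop one word: "documenting no PD after subsequent anti-cancer therapy is given".
- **New-therapy rule (SAP 9.6, with the same sentence in protocol 9.7.2).** "For PFS, PFS2 and DoR, a patient progressing after stopping current treatment and starting a new therapy will be censored" at the last progression-free assessment before the change.

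Neither document defines the term used in Table 5 and the prose. The nearest help is SAP section 12, which describes anti-cancer therapy after study treatment in general.

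**The concern.** PFS2 exists to count progression on second-line. A rule that censors that progression, or that leaves deaths before second-line without an outcome, estimates something else. Two programmers could each follow the SAP and report different medians and 24-month rates.

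PFS2 is a named secondary outcome and is analysed by subgroup. SAP section 18 lists its results table and its Censoring/Event Status table among the primary-analysis outputs, so the rules are needed at the first database lock. If they are settled while programming on accumulated data, the choice is no longer prespecified. The status table would show how many patients were censored, but not which rule was right.

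**Working it through.** The plan states no PFS2 figure to reproduce. The check sets the rules side by side and then illustrates the size.

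**Step 1. Classify patient histories under each rule.** Call the undefined therapy F.

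| History | Definition | Prose | Formula | Table 5 |
|---|---|---|---|---|
| Death, no prior PD, no second-line | Event | Event | No date | No row |
| First PD, then death, no second-line | Event | Event | No date | PD censored; death has no row; no date |
| PD on second-line, F = second-line | Event | Censored | Event | Event |
| PD on second-line, F = third-line | Event | Event | Event | Censored |
| PD after third-line started without PD on second-line (either F) | No event | Censored | Event | Event |
| Alive, no PD, still on first-line | No event | Censored at last assessment | – | Censored; no date |

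- F = third-line: the prose fits the definition, but Table 5 censors the defining event.
- F = second-line: Table 5 fits for PD on second-line, but the prose censors everyone who starts second-line without a prior event.
- Either way, deaths before second-line and the Table 5 censoring date remain unresolved.

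The rule in SAP 9.6 and protocol 9.7.2 censors PD on second-line if the current treatment is avelumab plus axitinib. It does not if the current treatment is second-line. The text does not say which.

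**Step 2. Patients with no Table 5 censoring date.** Protocol section 7 cites a median PFS of 13.3 months (95% CI 11.1-15.3) for the combination. With exponential times, the share free of PD and death on first-line at 24 months is 2^(-24/median):

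- 2^(-24/13.3) = 28.6%
- 2^(-24/11.1) = 22.3%
- 2^(-24/15.3) = 33.7%

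The other 71.4% have a first PD or death by then. If 10-30% of those were deaths without second-line (assumed), 7 to 21 patients per 100 would have no Table 5 row (71.4 × 0.10 = 7.1; 71.4 × 0.30 = 21.4).

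**Step 3. Effect on 24-month PFS2.** Simulation of 200,000 patients per scenario, with exponential times, Kaplan-Meier at 24 months and no other dropout. Only the 13.3-month median and the 24-month horizon come from the documents. Assumed inputs:

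- 15% of first-line PFS events are deaths.
- 50, 65 or 80% of progressors start second-line 1 month after PD.
- Second-line PFS has median 6 months; 25% of its events are deaths.
- 30 or 60% of second-line progressors start third-line 1 month after PD; median 4 months to PD or death on third-line.
- Median survival is 6 months after PD when no next line is given.
- Tumor assessment is every 3 months.

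| Rule applied | 24-month PFS2 |
|---|---|
| Definition | 45-46% |
| *All deaths counted* | |
| Table 5, F = second-line | 42-45% |
| Table 5, F = third-line | 49-53% |
| SAP 9.6 rule, current treatment = first-line | 50-58% |
| *Deaths before second-line dropped* | |
| Table 5, F = second-line | 57-68% |
| Formula alone | 60-73% |
| Table 5, F = third-line | 84-95% |

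Ranges run over the six combinations of second-line and third-line uptake. Independent re-runs agreed to within about 2 points, depending on coding choices. If a programmer set missing Table 5 dates to the index date under F = second-line, the result would be 13-19% (all deaths counted) or 27% (early deaths dropped).

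With wider inputs (second-line PFS 4-8 months, survival after PD 4-10 months, first-line deaths 10-20%), the shift is -6 to +17 points with all deaths counted. It is +7 to +54 points with early deaths dropped and valid censoring dates.

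**The case against.** The strongest reply is grammatical. The prose sentence could be read as covering patients who neither have an event nor start the therapy. With F = second-line, the prose, the formula and the first two rows of Table 5 would then agree on PD. But the PFS sentence is built the same way, and Table 4 settles its meaning: PD or death after a new therapy is censored. Table 5 does reverse Table 4's before/after logic, so the analogy is not conclusive. Even so, this reading leaves early deaths with no outcome row and patients who never start F with no Table 5 date.

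Several narrower points stand:

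- The prose supplies a usable censoring date, so the missing date arises only if Table 5 governs. Patients who start second-line after first PD do have a Table 5 date when F = second-line.
- The sentence in SAP 9.6 and protocol 9.7.2 is ambiguous rather than in proven conflict.
- No rule assigns the index date to patients with adequate follow-up assessments; footnote a in Table 5 covers only those without any. That scenario shows what a programmer might do with an empty date.
- With all deaths counted, the shift of -3 to +13 points is comparable to sampling error. At 100 patients the approximate 95% half-width is 1.96 × √(0.455 × 0.545 / 100) = 9.8 points. Sampling error, however, is not a reason to leave a systematic difference in place.
- The 13.3-month median comes from a trial, whereas the clock here starts after one or two cycles.

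**Conclusion.** The concern holds. The contradiction is visible in the text and does not depend on the simulation: no one meaning of the term brings the definition, formula, prose and Table 5 into agreement.

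The size depends mainly on how deaths before second-line are handled. Against 45-46% by definition, the shift in 24-month PFS2 is -3 to +13 points when all deaths count. It is +12 to +49 points when deaths before second-line are dropped and valid censoring dates are used. The upper end also needs F = third-line, which censors the endpoint's own defining event. Setting missing dates to the index date gives -18 to -33 points. These figures rest on assumed inputs and show direction and rough size only.

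PFS2 is secondary and descriptive, its subgroup analyses are exploratory, and the primary 12-month OS rate is untouched. The point should be fixed before the first lock, but it does not threaten the study's main result.

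**What to change.** In SAP 14.2:

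1. Define the term as therapy after second-line (third-line or later) and use it in every Table 5 row.
2. In the formula and in Table 5, make PD on second-line an event, and make death from any cause an event whether or not second-line was started.
3. Censor patients with no event at the last adequate tumor assessment. Name explicitly those still on first-line and those alive after first PD without second-line. Remove the requirement that the assessment follow the further therapy.
4. Keep censoring when third-line starts before PD on second-line, which is what the prose says once the term is defined this way. State that this qualifies death from any cause for deaths after third-line start. Counting those deaths would also be defensible, but the SAP must say which applies.

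In SAP 9.6 and protocol 9.7.2, either remove PFS2 from the new-therapy sentence or restate it there as the start of third-line.

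The cost is SAP wording, the programming specification and one protocol sentence. The protocol edit would follow the amendment route in protocol section 9.10.1. No new data are needed: the schedule of assessments already collects second-line treatment, third-line treatment and tumor response.

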#### 9.1.2.2 Secondary

Secondary effectiveness outcomes:

- OS rate at 24 months after the index date
  - Percentage of patients who are still alive at 24 months after the index date
- OS
  - Time interval from the index date to the date of death from any cause
- ORR up to 24 months after the index date
  - Percentage of patients with complete response (CR) or partial response (PR), as best overall response up to 24 months after the index date according to the investigator assessment

- DCR up to 24 months after the index date
  - Percentage of patients with CR, PR, or stable disease (SD), as best overall response up to 24 months after the index date according to the investigator assessment
- DoR
  - DoR is defined as the time from the first CR or PR criteria met, whichever was reported earlier, until the date of documented overall disease progression

**Note:** CR, PR, SD, progressive disease (PD) will be defined as per Response Evaluation Criteria in Solid Tumours (RECIST) version 1.1 ([Eisenhauer 2009](#))

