### **9.2.3                   Observation Period**

Each patient will be followed up from the date the ICF is signed until lost to follow-up, withdrawal of consent, death, or the end of the data collection period, whichever comes first. Patients will be followed up for 24 months from the index date, irrespective of whether they continue or discontinue the study treatment.

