### **9.7.2 Derived and Transformed Data**

Primary and secondary effectiveness outcomes will be derived as per definition reported in [Section 9.1.2](#).

For OS, PFS, PFS2 and DoR, the percentage of patients alive at the time of outcome assessment (12 or 24 months) will be calculated as per the Kaplan-Meier approach.

For PFS, PFS2 and DoR, a patient progressing after stopping current treatment and starting a new therapy will be censored at the latest tumor assessment showing no progression before changing therapy.

For safety, time to onset of AE will be calculated as difference in days between start date of AE and the index date +1, while duration of AE (applicable for resolved AEs only) will be calculated as difference in days between end date of AE and start date of AE +1.

Time to Avelumab plus Axitinib discontinuation will be derived as difference in days between last dose of Avelumab plus Axitinib and the index date +1 and time to second-line therapy after study treatment discontinuation will be calculated as difference in days between start date of second-line treatment and last dose of Avelumab plus Axitinib +1.

As per NCCN-FACT Fksi-19 scoring guidelines (version 2), the total HRQoL score (range 0-76) will be calculated as sum of single items scores multiplied by 19 and divided by the number of items completed. NCCN-FACT Fksi-19 will also cover 4 subscales: DRS-P (items from 1 to 11, range 0-48), DRS-E (item 12, range 0-4), TSE (items from 13 to 15, range 0-12) and FWB (items from 16 to 19, range 0-12). The higher the subscores or the total score, the better the HRQoL. The subscales will be evaluable, if at least 50% of respective items will be answered and will be calculated as sum of items included in the subscale, multiplied by the item included in the subscale, and divided by the item answered in the subscale. The Fksi-19 questionnaire as a whole will be evaluable, if all subscales will be evaluable and at least 80% of all items will be answered. Score of items 11 (C6), 12 (GF5), and from 16 to 19 (GF1, GF3 and GF7) will be reversed before calculating total and subscale scores.

Every effort will be made to capture all available data by:

- Ensuring that primary variables of interest are those that are routinely collected as part of routine clinical practice and are available via medical charts, physician, and/or patient/caregiver reporting, as appropriate

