To determine OS rate at 24 months after the index date	Endpoint: Percentage of patients who are still alive at 24 months after the index date.	14.2
To assess duration of OS	Endpoint: Time interval from the index date to the date of death from any cause.	14.2
To evaluate objective response rate (ORR) and disease control rate (DCR) up to 24 months after the index date	Endpoints: 
Percentage of patients with complete response (CR) or partial response (PR), as best overall response (BOR) up to 24 months after the index date according to the investigator assessment.Percentage of patients with CR, PR, or stable disease (SD), as BOR up to 24 months after the index date according to the investigator assessment. BOR will be derived as documented BOR considering the order CR>PR>SD>Progressive Disease (PD).	14.2
To assess duration of response (DoR)	Endpoint: for patients with BOR of CR or PR only, is the time interval from the first CR or PR criteria met, whichever was reported earlier, until the date of documented overall disease progression. BOR will be derived as documented BOR	14.2

Objectives	Endpoints (Outcome Measures)	IAP section
To assess duration of progression-free survival (PFS) on Avelumab plus Axitinib therapy and progression-free survival 2 (PFS2) on Avelumab plus Axitinib therapy followed by the second-line treatment	Endpoints: 
 Time interval from the index date to the date of disease progression or death from any cause, whichever comes first. Time interval from the index date to the date of disease progression on second-line treatment or death from any cause, whichever comes first. 	14.2
To assess the health-related quality of life (HRQoL)	Endpoint: National Comprehensive Cancer Network/Functional Assessment of Cancer Therapy-Kidney Symptom Index 19 (NCCN-FACT FKSI-19) at the index date and at every 6 weeks thereafter, until the end of treatment (EOT) or end of 24 months of study follow-up period, whichever occurs first.	16.3

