Anti-cancer therapy after end of study treatment will be summarized according to the respective eCRF page. Treatments will be categorized by means of coding and medical review. The same approach as for CMs will be applied based on ATC level 2 and PT.

Number and percentage of participants with any anti-cancer post study treatment and by type [(immunotherapy, targeted therapy, chemotherapy, radiotherapy, other)] will be presented.

Number and percentage of participants treated with targeted therapies, monoclonal antibodies and other protein kinase inhibitors as post study treatment (based upon ATC coding) will be presented including PT separately for:

- Anti-vascular endothelial growth factor (VEGFR, ATC code L01EK)
- Tyrosine kinase inhibitors (TKIs, ATC code L01EB)
- Mammalian target of rapamycin (mTOR, ATC code L01EG)
- Monoclonal antibodies (ATC code L01EX)
- Other protein kinase inhibitors (ATC code L01XC).

Summary statistics will be created for intent of therapy (Neo-Adjuvant / Adjuvant / Metastatic or Locally advanced), line number, duration, and best response across all post study treatments. For

participants who received more than one anti-cancer therapy after treatment discontinuation, the BOR among all anti-cancer therapies will be summarized.

13**Study Treatment: Compliance and Exposure**

The following analyses will be performed based on the analysis set for Avelumab and Axitinib by visit.

All dosing calculations and summaries will be based on “Avelumab Administration” and “Axitinib Administration” eCRFs pages.

No imputation of missing start dates of study treatments will be done.

In case the last date of study drugs is incomplete the date of last study drugs administration will be taken from the EOT page. A dose is regarded to be administered if the actual dose received is > 0.

Exposure duration and cumulative dose for each treatment of the combination will be summarized after being derived in days respectively as difference between last treatment date–index date +1, for Axitinib (days unit) and (last treatment date – index date +14) for Avelumab and the sum of the actual doses of study drugs received overall. For Avelumab, duration will also be expressed in terms of cycles and derived as (last treatment date – index date +14)/14 considering each cycle duration of 2 weeks.

The summary of treatment exposure will include the following information:

- Exposure duration (days/cycles)
- Cumulative dose (milligrams)

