	
DoR (months) = [date of event or censoring–date of first CR or PR +1]/30.4375
 
DoR will be estimated by the KM method. The percentage of censored patients will also be reported. Median event time will be reported, along with 25th and 75th percentiles. Percentage of patients experiencing event or being event-free at applicable timepoints will also be reported along with the corresponding two-sided 95% CIs.

Table 6 **Outcome and event dates for DoR**

Scenario	Date of event/censoring	Outcome
PD before subsequent anti-cancer therapy	Date of PD	Event
PD after subsequent anti-cancer therapy	Date of last adequate tumor assessment ^a documenting no PD before subsequent anti-cancer therapy is given	Censored
No PD/Death	Date of last adequate tumor assessment ^a documenting no PD/Death before subsequent anti-cancer therapy is given	Censored
Treatment discontinuation due to 'Disease progression' without documented progression	Not applicable	Information is ignored. Outcome is derived based on documented progression only.
Study end for consent withdrawn without PD	Date of last adequate tumor assessment ^a documenting no PD before subsequent anti-cancer therapy is given	Censored
Study end for lost to follow-up without PD	Date of last adequate tumor assessment ^a documenting no PD before subsequent anti-cancer therapy is given	Censored

^a If there are no adequate post-baseline assessments prior to the PD, then the time without adequate assessment should be measured from the index date; if the criteria were met the censoring will be on the index date.

T2LT

T2LT is defined as the time from the last dose of Avelumab plus Axitinib to the start date of second-line treatment for RCC.

	T2LT time (in months) = (Second-line treatment start date – last dose of Avelumab plus Axitinib + 1)/ 30.4375 (months)
--	--

	T2LT will be summarized by descriptive statistics for continuous variables.
--	---

The subgroup analyses will be performed on selected secondary endpoints (OS, DCR, PFS, and PFS2) based on the analysis set for all subgroup levels defined in [Section 8.2](#) “Subgroup definition and parametrization”. All the subgroup analyses are exploratory and will be performed unstratified.

No adjustment for multiplicity will be performed. In the case of a low number of participants within a category of the analysis set, the categories will be pooled when meaningful (see [Section 8.2](#)).

15 Safety Analyses

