16.4 Further Other Endpoints

Not applicable.

17**References**

18 Appendices

List of outputs included in primary analysis.

Output Number	Output Title
Table 8.1.1.1	Subject Disposition Status
Table 8.1.1.3	Analysis Sets
Table 8.1.4.1	Demographics and Baseline Characteristics
Table 8.1.5.1	Medical History
Table 8.1.6.1	Disease History
Table 8.1.6.2	ECOG Performance Status
Table 8.1.7.1	Previous Medication
Table 8.1.7.3	Concomitant Medication
Table 8.1.7.2.1	Prior Anti-Cancer Drug Therapies
Table 8.1.7.2.2	Prior Anti-Cancer Drugs
Table 8.1.7.2.3	Prior Anti-Cancer Surgeries
Table 8.1.7.2.4	Prior Anti-Cancer Radiotherapies
Table 8.1.8.1.1	Duration of Therapy
Table 8.1.8.2	Cumulative Dose, Dose Intensity, Relative Dose Intensity
Table 8.1.8.4	Dose Reduction
Table 8.2.1.1	Primary analysis, Overall Survival Rate at 12 Months
Table 8.2.1.2	[REDACTED]
Table 8.2.1.3	Subgroups Analysis: Primary Analysis, Overall Survival Rate at 12 Months by Subgroups
Table 8.2.2.1.2	Overall Survival, Censoring/Event Status Limited to 12 Months of Observation
Figure 8.2.2.2	Overall Survival Limited to 12 Months of Observation

Table 8.2.2.4.1	Progression Free Survival
Table 8.2.2.4.2	Progression Free Survival, Censoring/Event Status
Table 8.2.2.7.1	Progression Free Survival to 2 nd Line of Treatment
Table 8.2.2.7.2	Progression Free Survival to 2 nd Line of Treatment, Censoring/Event Status
Table 8.2.2.10.1	Objective Response Rate and Disease Control Rate up to 12 Months
Table 8.2.2.10.2	[REDACTED]
Table 8.2.2.12.1	Duration of Response up to 12 Months
Table 8.2.2.12.2	[REDACTED]
Table 8.2.2.12.3	Duration of Response up to 12 Months, Censoring/Event Status
Table 8.2.2.13	Time to 2nd Line Treatment
Table 8.3.1.1	Overview of Treatment-Emergent Adverse Events
Table 8.3.1.2	Overview of TEAEs Leading to Discontinuation
Table 8.3.1.3	TEAEs by Primary System Organ Class (SOC) and Preferred Term (PT)
Table 8.3.1.7	Serious TEAEs by Primary System Organ Class (SOC) and Preferred Term (PT)
Table 8.3.1.8.1	Related TEAEs by Primary System Organ Class (SOC) and Preferred Term (PT)

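### The readable best-response rule for ORR and DCR does not stop at first progression or new therapy, so a second-line PR or SD can be credited to avelumab plus axitinib

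*SAP*

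**What the plan says.** Protocol Section 9.1.2.2 defines ORR and DCR as the percentage of patients with CR or PR, or with CR, PR or SD, "as best overall response up to 24 months after the index date according to the investigator assessment". SAP Section 5 gives the same definition and ranks the documented categories from CR down to PD. SAP Section 14.2 repeats the rule: "Investigator response will be used to determine the BOR up to 24 months derived as per documented BOR considering the order CR>PR>SD>PD". SAP Section 7 comments on this window, but only to change it from at 24 months to up to 24 months. The appendix list of primary-analysis outputs applies a shorter calendar window: "Objective Response Rate and Disease Control Rate up to 12 Months".

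Protocol Section 9.2.3 follows patients for 24 months "irrespective of whether they continue or discontinue the study treatment". In protocol Table 1, treatment response and second-line treatment are marked in the same columns (follow-up visits and week 104). PFS2 in SAP Section 14.2 relies on investigator RECIST assessment during second-line treatment.

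The new-therapy rule, in protocol Section 9.7.2 and again in SAP Section 9.6, begins: "For PFS, PFS2 and DoR, a patient progressing after stopping current treatment and starting a new therapy will be censored". ORR and DCR are not named. For DoR, SAP Table 6 counts "PD before subsequent anti-cancer therapy" as an event and otherwise censors at the last adequate scan before the new therapy.

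**The concern.** The study aim is the effectiveness of avelumab plus axitinib as first-line therapy. A best-category rule that runs over calendar time, in a study that keeps recording response on later lines, mixes the effect of later drugs into ORR and DCR. A maximum taken over more assessments can rise but cannot fall, so the distortion goes one way.

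DCR is also reported by subgroup, and both rates appear in the 12-month outputs. A programmer who follows the text and one who assumes a first-line cut would derive different ORR, DCR and DoR sets from the same data. DoR has a further problem: patients are selected by the uncut best response, but the end dates in Table 6 presume that the response came before any new therapy.

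**Working it through.** **Rule applied to short sequences.** The second column takes the highest category up to 24 months. The third stops at first PD or new therapy.

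| Documented sequence | As written | With the stop | Change |
|---|---|---|---|
| First line PD; second line PR | PR | PD | leaves ORR and DCR |
| First line PD; second line SD | SD | PD | leaves DCR |
| First line SD, then PD; second line PR | PR | SD | leaves ORR |
| First line SD; new therapy without PD, then PR | PR | SD | leaves ORR |
| First line PR, then PD | PR | PR | none |

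**DoR.** The SAP formula is (date of event or censoring − date of first CR or PR + 1)/30.4375. Illustrative dates: PD on day 120, second line from day 140, first PR on day 230. The uncut rule makes this patient a responder, and Table 6 sets the event at day 120:

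(120 − 230 + 1)/30.4375 = −109/30.4375 = −3.6 months.

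If there was no earlier PD, Table 6 censors at the last adequate scan before the new therapy, which also precedes the response.

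**Size for ORR.** The plan states no expected ORR or DCR for this study, so there is no figure to reproduce. The 51.4% is the JAVELIN Renal 101 ORR quoted in protocol Section 7, and the study size of about 100 is from protocol Section 9.5. All other inputs are assumptions.

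Rise in ORR = (1 − first-line ORR) × share of non-responders starting second line × second-line ORR × share assessed in time.

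- First-line ORR 45% or 51.4%; uptake 30, 40 or 50%; second-line ORR 15, 25 or 35%; assessed 50, 75 or 100% (54 combinations).
- Lowest: 0.486 × 0.30 × 0.15 × 0.50 = 1.1 points.
- Highest: 0.55 × 0.50 × 0.35 × 1.00 = 9.6 points. Median 3.5.
- All patients assessed: 2.2 to 9.6 points.
- Mid case at 51.4%: 0.486 × 0.40 × 0.25 = 4.9 points if all are assessed, and × 0.75 = 3.6 points. The reported ORR would be 55.0 to 56.3%.
- 12-month output, uptake 10 to 30%: 0.4 to 5.8 points, median 1.7.

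For scale, the Clopper-Pearson 95% interval at 51/100 is 40.8 to 61.1%, a half-width of 10.2 points.

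**Size for DCR.** Rise = share with PD as best first-line response (10 to 20%) × second-line uptake (40 to 70%) × share with at least SD on second line (40 to 70%) × share assessed (50 to 100%).

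- Lowest: 0.10 × 0.40 × 0.40 × 0.50 = 0.8 points.
- Highest: 0.20 × 0.70 × 0.70 × 1.00 = 9.8 points. Median 3.0.

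**Sensitivity to the assumptions.** Take 51 responders in 100, 20 to 60% of the other 49 assessed on second line, and 10 to 40% of those responding. ORR then rises by 49 × 0.2 × 0.1 = 1.0 to 49 × 0.6 × 0.4 = 11.8 points. For DCR, with first-line DCR 75 to 85% and 40 to 80% for each of the other two factors, the rise is 15 × 0.4 × 0.4 = 2.4 to 25 × 0.8 × 0.8 = 16 points. The direction is fixed; the size depends on the inputs.

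**The case against.** The strongest objection is redaction. In SAP Section 14.2, hidden text follows the best-response sentence under ORR, DCR and DoR, which is where a stop rule could sit. The modification history suggests that the hidden text concerns confirmed response, but that is an inference. This limits certainty. It does not remove the point, because protocol Section 9.1.2.2 and SAP Section 5 are readable and state the rule without a stop.

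RECIST 1.1 governs response and might be thought to close the window at PD. The protocol cites it for the response categories, and neither document writes out a period for best response. The confirmation table in the SAP appendix has no row starting at PD. That would fit a sequence that closes at PD, but the table does not say so.

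SAP Section 12 summarises later-line response from its own eCRF page: for patients with several later therapies, "the BOR among all anti-cancer therapies will be summarized". If second-line responses were recorded only there, ORR and DCR would escape. But PFS2 needs second-line tumour assessments, and nothing excludes these from ORR or DCR.

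On DoR, a progression before a response is not naturally the end of that response, so Table 6 was probably written with first-line responders in mind. That is fair evidence of intent, but the readable text does not carry it out.

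Two objections stand in full. The size is almost wholly assumed, and the mid case is under half the confidence half-width. ORR and DCR are also descriptive secondary outcomes in a single-arm study with exploratory subgroups.

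**Conclusion.** The concern holds on the readable text. The stated rule credits second-line PR or SD to first-line avelumab plus axitinib, and no readable passage supplies a cut-off. Under the assumed inputs the upward bias is 1.1 to 9.6 points for ORR (mid case 3.6 to 4.9) and 0.8 to 9.8 points for DCR. The upper ends need every input at its extreme. The mid case lies well inside the sampling error at about 100 patients, but it is a systematic error that a larger sample would not remove. DoR can also receive negative values.

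The 12-month OS endpoint is untouched and no formal comparison depends on these rates. This should be corrected, but it does not threaten the main result. Confidence is medium because of the redactions.

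**What to change.** In protocol Section 9.1.2.2 (and the matching abstract text) and SAP Sections 5 and 14.2, define best overall response for ORR, DCR and entry to the DoR set as the best investigator-documented response from the index date to the earliest of:

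- first documented PD;
- start of subsequent anti-cancer therapy;
- 24 months (12 months for the primary-analysis outputs).

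Use later assessments only for PFS2 and the later-line summaries. Give subsequent anti-cancer therapy the same meaning here as in SAP Tables 4 and 6, and state it: SAP Section 9.9 includes radiation and other therapy under that term, whereas the on-treatment period in Section 9.8 refers to drug therapy only. If the redacted text already contains this stop, it is enough to confirm that and align the readable definitions.

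The cost is one sentence in each document and one date filter in the derivation, with no new data. Reported ORR and DCR may be lower than under the present wording. A response first recorded after PD while the patient is still on avelumab plus axitinib would also no longer count, in line with how PFS and DoR already treat first PD.
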